### **3.8 Safety Analyses**

Safety assessments will be based on the incidence, severity, and type of adverse events, and clinically significant changes in the subject's clinical laboratory tests, vital signs, ECGs, and physical examinations.

#### **3.8.1 Adverse Events**

Adverse events will be coded using the MedDRA adverse event coding system for purposes of summarization. All adverse events reported will be listed in the data listings. Treatment emergent adverse events (TEAEs) will be tabulated. A treatment-emergent AE (TEAE) is any AE that starts on or after the first dose of study drug through the end of the treatment period or any event that is considered drug related regardless of the start date, or any event which occurs prior to the first dose of study drug and worsens in severity after the first dose of study drug. An AE is considered drug related if it is possibly related or probably related to study drug.

TEAEs will also be tabulated by whether events are considered related to treatment and by severe severity. Serious adverse events and TEAEs resulting in study discontinuation will be tabulated.

Summarization of AEs will include subject incidence of the following:

- All TEAEs
- Drug-related TEAEs

- Severe TEAEs
- Severe and drug-related TEAEs
- Serious Adverse Events (SAEs)
- Drug-related SAEs
- Death due to AEs
- TEAEs leading to study drug discontinuation
- Drug-related TEAEs leading to study drug discontinuation

An overall summary table will contain the number and percentage of subjects ever having one of the above listed subsets of AEs. All TEAEs will be summarized for each treatment group by MedDRA system organ class (SOC), by SOC and preferred term (PT), and by PT with the number and percentage of subjects. If a subject has more than 1 occurrence of the same TEAE, he/she will be counted only once within that preferred term and system organ class in the summary tables. The most severe occurrence of a repeat TEAE, as well as the most extreme relationship of the TEAE to the study drug will be used for the analyses.

TEAEs related to study drug, severe TEAEs, serious adverse events (SAEs), and TEAEs leading to study drug discontinuation will be summarized in the same manner. That is, summaries will be provided for the numbers and percentages of subjects by SOC, SOC and PT, and PT.

All AEs will be included in by-subject listings. Specific by-subject listings of SAEs and TEAEs leading to study drug discontinuation will be provided. The number of days between first dose and when the event occurred will be presented in listings as well (i.e., relative study day), as will duration of the AE.

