8.2.7 Evaluations and procedures at Visit 8 (Day 141 ± 3)

- Concurrent Medications (changes since last visit)
- Vital Signs
- Adverse Events
- Treatment Satisfaction PRO
- Drug Returned
- Drug Dispensed (two bottles are dispensed)
- IVRS Training/Compliance Check & Reminder

8.2.8 Evaluations and procedures at Visit 9 (Day 183 ± 3) and Early Termination Visits

- Concurrent Medications (changes since last visit)
- Physical Exam
- Vital Signs
- Serum Chemistry and Hematology
- Pharmacogenomics blood sample (if consented and not performed at Visit 4 or 6)
- Biomarker sample
- Urine Pregnancy Test
- Urinalysis
- ECG
- Adverse Events
- IBS-QOL PRO
- Treatment Satisfaction PRO
- Drug Returned

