9.4. Causality

Association of adverse events to the study drug will be made using the following definitions:

Not related: The event is most likely produced by other factors such as the subject's clinical condition, intercurrent illness, or concomitant drugs, and does not follow a known response pattern to the study drug, or the temporal relationship of the event to study drug administration makes a causal relationship unlikely

Possibly-related: The event follows a reasonable temporal sequence from the time of drug administration, and/or follows a known response pattern to the study drug, but could have been produced by other factors such as the subject's clinical condition, intercurrent illness, or concomitant drugs

Probably-related: The event follows a reasonable temporal sequence from the time of drug administration, and/or follows a known response pattern to the study drug, and cannot be reasonably explained by other factors such as the subject's clinical condition, intercurrent illness, or concomitant drugs.

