9.6. Procedures for Recording and Reporting AEs and SAEs

Adverse events, both serious and non-serious, will be reported between Day 1 (Randomization) and the final visit (up to Day 183, Visit 9). Medical events that occur between the signing of the informed consent and the first dose of study drug will be documented as part of the subject's medical history and recorded on the appropriate eCRF page.

All adverse events spontaneously reported by the subject and/or in response to an open question from study personnel or revealed by observation, physical examination or other diagnostic procedures will be recorded on the appropriate page of the eCRF. Any clinically relevant deterioration in laboratory tests or other clinical finding is considered an adverse event and must be recorded on the appropriate pages of the eCRF. When possible, signs and symptoms indicating a common underlying pathology should be noted as one comprehensive event or diagnosis.

All serious adverse events occurring during the course of the study must be reported by email, or fax immediately to:

In no event shall a SAE be reported more than twenty-four (24) hours after the Investigator becomes aware of such event. The report of an SAE by the Investigator must provide the following minimal information: protocol number, subject number, subject's initials and date of birth, nature of the adverse event and attributes such as the severity of the event and causality. Events will be considered suspected adverse drug reactions if classified by the Investigator as possibly-related or probably-related.

A report of a SAE by telephone must always be confirmed by a written, more detailed report within 24 hours of the Investigator becoming aware of the event. The SAE Reporting Forms are provided to each clinical study site in the Study Manual. The Investigator should provide the following documentation at the time of notification, if available:

- SAE Reporting Form
- Concomitant and support medication pages;
- Relevant diagnostic reports;
- Relevant laboratory reports;
- Admission notes; if applicable

Hospital discharge summary; if applicable

Ardelyx will assume responsibility for appropriate reporting of adverse events to regulatory authorities. Ardelyx will report Suspected Unexpected Serious Adverse Reactions (SUSARs) to all investigational sites.

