10.7.7 Safety Analyses

Safety assessments will be based on the incidence, severity, and type of adverse events, and clinically significant changes in the subject's clinical laboratory tests, vital signs, ECGs and physical examinations.

Adverse events will be coded using the MedDRA adverse event coding system for purposes of summarization. All adverse events reported will be listed in the data listings. Treatment emergent adverse events (TEAEs) will be tabulated, where treatment emergent is defined as any adverse event which occurs after administration of the first dose of study drug and up through the final visit (up to planned Day 183), any event that is considered drug-related regardless of the start date of the event, or any event that is present at baseline but worsens in severity or is subsequently considered drug-related by the investigator. TEAEs will also be tabulated by whether events are considered related to treatment (possibly or probably drug-related, or unknown in relationship) and by severity. Serious adverse events and TEAEs resulting in study discontinuation will be tabulated.

Actual values and change from baseline values for clinical laboratory tests will be summarized for each visit collected during the study. The frequency of clinically significant abnormal laboratory test values will be tabulated by treatment group. Shift tables will be derived for changes in laboratory tests from screening to Visit 4, 6, and 9.

Vital signs will be summarized descriptively for actual values and change from baseline values by treatment group and visit. Vital signs are collected at all study visits during the screening period and 26-week treatment period. Baseline for the vital signs will be the average of results obtained during the screening period.

Electrocardiogram results will be summarized descriptively for actual values and change from screening values by treatment group and visit (Screening (Visit 1/Day -14), Week 12 (Visit 6/Day 85), and Week 26 (Visit 9/Day 183)). The overall interpretation will be summarized with number of subjects and percentages for the normal and abnormal ECG result categories.

All vital signs and electrocardiogram results will be listed. Abnormal or clinically significant results will be flagged.

Physical examinations are collected at Screening (Visit 1/Day -14) and Week 26 (Visit 9/Day 183). The number and percentage of subjects in each category will be presented for each visit by treatment group.

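### SAP 3.8.1 departs without explanation from protocol 10.7.7 on which adverse events count as drug-related and on when the treatment-emergent window closes

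*SAP*

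**What the plan says.** **Relationship.** Protocol 10.7.7 has TEAEs tabulated by relationship, with the related group described as "possibly or probably drug-related, or unknown in relationship". SAP 3.8.1 gives a narrower rule: "An AE is considered drug related if it is possibly related or probably related to study drug". It mentions neither unknown nor missing relationship.

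The investigator's scale is in protocol 9.4 ("Association of adverse events to the study drug will be made using the following definitions"). It has three grades: not related, possibly related and probably related. For safety reporting, protocol 9.6 adds: "Events will be considered suspected adverse drug reactions if classified by the Investigator as possibly-related or probably-related".

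**Window.** Protocol 10.7.7 counts events after the first dose "up through the final visit (up to planned Day 183"). The visit concerned is described in protocol 8.2.8: "Evaluations and procedures at Visit 9 (Day 183 ± 3) and Early Termination Visits". SAP 3.8.1 counts an event that "starts on or after the first dose of study drug through the end of the treatment period", and does not say what date that end point is. Both documents also treat a drug-related event as a TEAE whatever its start date.

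**Authority to change.** Protocol Section 10 allows the SAP to alter the statistical section without a protocol amendment, and expects the SAP to address any such alteration. SAP 3.8.1 does not mention that either definition differs from the protocol.

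**The concern.** Safety and tolerability are the secondary objective in both documents, and the summary tables in SAP 3.8.1 are where incidence will be read.

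The protocol's clause on unknown relationship is the only rule in either document for an event without a usable causality rating. Once it is removed, such an event does not satisfy the SAP's definition. The SAP does supply rules for other gaps: missing medication dates (3.6.3) and a missing last-dose date (3.6.4). It has none here.

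The window has a similar gap. The protocol ties it to a visit, which every completer has and which early terminators are also asked to attend. The SAP ties it to a period whose end is not stated for a subject who stops early. The SAP's compliance formula (3.6.4) divides tablets used by two times the days in the treatment period. That is a sensible expected count only if those are dosing days, so a programmer could reasonably take the period to end at last dose. Two programmers working from the present text could produce different TEAE tables.

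**Working it through.** The plan states no figure on this point, so the check is a comparison of texts plus some day arithmetic.

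**1. Relationship rule.**
- Protocol set: {possibly, probably, unknown}. SAP set: {possibly, probably}. The second lies inside the first, and they differ by the events of unknown relationship.
- SAP 3.8.1 lists nine summaries. Four use the drug-related definition: drug-related TEAEs, severe and drug-related TEAEs, drug-related SAEs, and drug-related TEAEs leading to discontinuation of study drug.
- Hold the window fixed, and let k be the number of subjects in an arm whose only qualifying events in a summary lack a usable rating. Then SAP count = count with the unknown clause − k, with k ≥ 0. The count cannot rise.
- For scale only, with 300 per arm (protocol 10.1) and assumed k, the fall in percentage points is 100 × k / 300. This gives k = 0: 0; k = 1: 0.33; k = 3: 1.0; k = 6: 2.0. The documents give no basis for choosing k.

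**2. Window, completers.** Visit 9 is on Day 183 ± 3, so V runs from Day 180 to Day 186. Let E be the day the treatment period ends. Days inside the protocol's window but outside the SAP's = max(0, V − E). SAP 3.8.1 does not give E. The efficacy week definitions are used here only to bound it: protocol 10.6 has Week 26 as Days (26 − 1) × 7 + 1 = 176 to 26 × 7 = 182, and SAP 3.5 runs Weeks 13 to 26 to Day 183.

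| End of period, E | V = 180 | V = 183 | V = 186 |
|---|---|---|---|
| Day 182 | 0 | 1 | 4 |
| Day 183 | 0 | 0 | 3 |
| Visit 9 itself | 0 | 0 | 0 |

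**3. Window, early terminators.** If E is the early-termination visit, the gap is zero. If E is the last dose, the gap runs from last dose to that visit, and the documents do not give its length. Protocol 9.6 collects events in that interval. The SAP would keep those rated possibly or probably related, because such events count whatever their start date. What would be left out is a new event that starts after last dose and is not so rated.

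**4. Where the window bears.** It bears directly on three summaries: all TEAEs, severe TEAEs, and TEAEs leading to discontinuation. Total SAEs and deaths carry no TEAE restriction. So 4 (relationship) + 3 (window) + 2 (neither) = 9.

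**5. Both together.** A late event with no usable rating would fail both SAP tests and leave the TEAE tables. That requires the last-dose reading and a missing or unknown rating at once.

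**The case against.** There is a fair case that little or nothing is lost.

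- The protocol lets the SAP change Section 10.
- Protocol 9.4 has no unknown grade, so the dropped clause may have nothing to act on. Protocol 9.6 uses the same two grades as the SAP for suspected reactions and requires causality in SAE reports.
- The SAP is silent on missing causality; it does not say that such events are unrelated.
- On the window, SAP 2.3.1 places Visit 9 at the end of the 26-week treatment period, and the SAP schedule puts the Visit 9/early-termination column under the treatment period.
- At its start, the SAP's window is no narrower than the protocol's.
- Every event appears in the by-subject listings, and the rules are the same in both arms.

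All of this stands and limits the size. It does not say how an event without a rating is to be tabulated, nor does it fix the closing date for an early terminator. Protocol 9.6 classifies suspected reactions for reporting; the tabulation rule in 10.7.7 is separate.

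A reader might go further in four ways that the documents do not support:

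- *That the SAP limits adverse events to first through last dose.* The sentence in SAP 3.5 that says so governs the derivation of efficacy weeks, and protocol 10.6 contains it too.
- *That the protocol itself cuts events off at Day 183.* That is the nominal day of the final visit. Protocol 9.7 runs through that visit, and 8.3.1.1 through the end of the study.
- *That subjects who stop because of an adverse effect lose that event.* An event that causes stopping normally starts on or before the last dose, so it is a TEAE on any reading.
- *That a number of affected subjects can be given.* The documents state no dropout rate, and an early terminator is not the same as a subject with a lost event.

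**Conclusion.** The concern holds in a limited form. Both departures are in the text and neither is explained.

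The relationship rule is the firmer part. Read literally, the SAP leaves an event of unknown or missing relationship out of four of nine summaries, where the protocol counts unknown relationship as related. The direction is certain (the same count or lower, in both arms). The size cannot be computed, and it may be nil to small because unknown can arise only from a missing or non-standard assessment.

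The window is an ambiguity and has not been shown to be shorter. It costs nothing if the period ends at Visit 9 or the early-termination visit. For completers it costs at most 4 days under the calendar readings above. For early terminators under a last-dose reading the cost is unknown, and it is confined to late events not rated related.

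It would be wrong to conclude that the two changes lower the reported harm. Neither has been shown to remove an event, and the listings keep every one. The point still merits correction, because it concerns a stated secondary objective and the present text allows different tables from the same data.

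**What to change.** In SAP 3.8.1, before unblinding:

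1. Define drug-related as possibly related, probably related, or of unknown relationship, and state that a missing causality assessment is counted the same way. The protocol speaks only of unknown, so the sentence on missing assessments is an addition and should be identified as one.
2. Define the TEAE window as onset on or after the first dose through the actual date of the subject's Visit 9 or early-termination visit. Keep the existing limbs for drug-related events and for events that worsen.

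The cost is two clauses in the SAP and the matching programming; no new data are needed. The downside is that related-event and TEAE counts may become slightly less favourable.

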9.2. Severity

The term “severe” is used to describe the intensity (severity) of a specific event (as in mild, moderate, or severe myocardial infarction). Even though the event itself may be of relatively minor medical significance (such as a severe headache), this is not the same as “serious,” which is based on subject/event outcome or action criteria as described above and are usually associated with events that pose a threat to a subject’s life or functioning. A severe adverse event is not necessarily serious. For example, persistent nausea of several hours duration may be considered severe nausea but not meet the definition of a SAE. On the other hand, a stroke resulting in only a minor degree of persistent disability may be considered mild, but would be defined as a SAE based on the above noted criteria. Seriousness (not severity) serves as a guide for defining regulatory reporting obligations.

For both serious and non-serious adverse events, the Investigator must determine the severity of the event using the following definitions:

Mild The event does not interfere in a significant manner with the subject’s normal functioning level. It may be an annoyance but does not cause any limitation in usual activity.

Moderate The event produces some impairment of functioning but is not hazardous to health. It is uncomfortable or an embarrassment and may cause some limitation in usual activity.

Severe The event produces significant impairment or incapacitation and is a definite hazard to the subject’s health.

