### **3.8.2 Clinical Laboratory Tests**

The list of clinical laboratory tests collected for this study are presented in Appendix C of the protocol. Serum chemistry, hematology, and urinalysis results will be summarized with descriptive statistics at Screening (Visit 1/Day -14), Week 4 (Visit 4/Day 29), Week 12 (Visit 6/Day 85), and Week 26 (Visit 9/Day 183) by treatment group. For continuous tests, actual values and change from screening will be summarized. For categorical tests, the number and percentage of subjects in each category will be presented for each visit. Serum chemistry tests included in these summaries will be albumin, alkaline phosphatase, ALT, AST, bicarb/CO2, total bilirubin, direct bilirubin, indirect bilirubin, calcium, chloride, total cholesterol, creatinine, glucose, inorganic phosphorous, LDH, potassium, total protein, sodium, triglycerides, BUN/urea, and uric acid. Hematology tests included in these summaries will be WBC, RBC, MCV, MCH, MCHC, hemoglobin, hematocrit, and platelet count. Differentials consisting of bands, monophils, neutrophils, eosinophils, lymphocytes, and basophils will be included in the listings only. Urinalysis tests included in these summaries will be appearance, specific gravity, and pH. Protein, glucose, ketones, blood, nitrite, and microscopic results will be presented in listings only.

The frequency of clinically significant abnormal laboratory test values will be tabulated by treatment group.

Shift tables classifying normal range results (low out of normal range, normal, or high out of normal range) between Screening and Week 4 (Visit 4/Day 29), Week 12 (Visit 6/Day 85), and Week 26 (Visit 9/Day 183) values will be tabulated by treatment group. Missing results for each pairwise summary will be tabulated.

Data listings of clinical laboratory tests will include flags for abnormal results.

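### The SAP tabulates only severe TEAEs where the protocol calls for tabulation by severity, and takes 12 of 44 laboratory tests out of the by-visit summaries, without declaring either change

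*SAP*

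**What the plan says.** **Adverse events.** For serious and non-serious events alike, Protocol 9.2 states that "the Investigator must determine the severity of the event using the following definitions" and then defines mild, moderate and severe. Protocol 10.7.7 states: "TEAEs will also be tabulated by whether events are considered related to treatment (possibly or probably drug-related, or unknown in relationship) and by severity". SAP 3.8.1 states: "TEAEs will also be tabulated by whether events are considered related to treatment and by severe severity". The SAP's list of incidence summaries has two severity entries, severe TEAEs and TEAEs that are both severe and drug-related. For the layouts by system organ class (SOC) and preferred term (PT), it adds: "TEAEs related to study drug, severe TEAEs, serious adverse events (SAEs), and TEAEs leading to study drug discontinuation will be summarized in the same manner".

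**Laboratory tests.** Protocol 10.7.7 states: "Actual values and change from baseline values for clinical laboratory tests will be summarized for each visit collected during the study" and "Shift tables will be derived for changes in laboratory tests from screening to Visit 4, 6, and 9". Neither sentence exempts a test. SAP 3.8.2 opens by promising descriptive summaries of chemistry, hematology and urinalysis at each scheduled visit, with counts and percentages for categorical tests. It then makes two exceptions: "Differentials consisting of bands, monophils, neutrophils, eosinophils, lymphocytes, and basophils will be included in the listings only" and "Protein, glucose, ketones, blood, nitrite, and microscopic results will be presented in listings only". The same section keeps a by-arm tabulation of clinically significant abnormal values, and shift tables against the normal range. Neither provision names an excluded test.

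**Authority to change.** The introduction to Protocol Section 10 says that changes to that section will be dealt with in the SAP and not by protocol amendment.

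**The concern.** Safety and tolerability form the secondary objective (Protocol 3.2), and SAP 2.1.2 gives tolerability its own bullet. Protocol Section 2 describes a drug whose proposed action raises fluid volume in the gut, so gastrointestinal events over 26 weeks are an obvious tolerability question. Under Protocol 9.2, the step from mild to moderate is the step from no significant interference with normal functioning to some impairment. A severe-only table does not show how the arms differ on that step. SAP 3.8 itself still says that safety assessment rests partly on the severity of events.

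On the laboratory side, summarizing the total white-cell count without its components can hide opposing movements in them. A difference between arms in urine protein, glucose or blood is hard to see in listings for about 600 subjects.

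Both points narrow what the protocol promises, and a reader of the SAP is not told so.

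**Working it through.** The plan states no figure on this point. The check is a comparison of texts and a count of tests.

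**Step 1: severity grades.**

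| | Mild | Moderate | Severe |
|---|---|---|---|
| Graded by investigator (Protocol 9.2) | yes | yes | yes |
| Tabulated under Protocol 10.7.7 | yes | yes | yes |
| Tabulated under SAP 3.8.1 | no | no | yes |

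The odd phrase in the SAP could be a slip for tabulation by severity. The list of summaries that follows argues against that, because it too names only the severe grade.

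**Step 2: what can be recovered from the planned tables.** Count each subject once at the worst grade, as SAP 3.8.1 already requires for repeated events. For any PT in either arm:

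N(all) = N(mild) + N(moderate) + N(severe)

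The planned tables give N(all) and N(severe), so N(mild) + N(moderate) = N(all) − N(severe). That is one equation in two unknowns: the sum is recoverable, the split is not. For drug-related events by SOC and PT, even the sum is not assured, because the sentence extending that layout to subsets does not name the severe and drug-related group.

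**Step 3: laboratory tests** (Protocol Appendix C against SAP 3.8.2).

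| Panel | Tests | Summarized by visit | Listings only |
|---|---|---|---|
| Serum chemistry | 21 | 21 | 0 |
| Hematology | 14 | 8 | 6 |
| Urinalysis, without urine hCG | 9 | 3 | 6 |
| Total | 44 | 32 | 12 |

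12 / 44 = 27%. Serology and FSH are also left out of the count.

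**Step 4: what remains for the 12 tests.**
- By-subject listings with abnormal results flagged (SAP 3.8.2).
- The by-arm tabulation of clinically significant abnormal values, with no test excluded by name.
- Clinically relevant laboratory deterioration recorded as an adverse event (Protocol 9.6), and so counted in the TEAE tables.
- Shift tables: unclear. The shift sentence excludes nothing, but confining a test to listings, read plainly, keeps it out.

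**Step 5: is either change declared?** Neither SAP 3.8.1 nor 3.8.2 calls its wording a departure from the protocol or gives a reason. The SAP's table of contents shows no section on changes from the protocol.

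**The case against.** **The SAP is allowed to do this.** A reader might infer a breach of the protocol. The documents do not support that: Section 10 lets the SAP change statistical considerations without an amendment, and its statement that analyses will stay the same covers the primary and key secondary analyses. What stands is that Section 10 expects changes to be addressed in the SAP, and these are made silently.

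**Most of the information is still reported.** A reader might infer that the 12 tests get no by-arm output, or that a signal in them could not be seen. Step 4 shows otherwise. Nor can it be said that the tests are definitely out of the shift tables. What stands is narrower. Clinical significance is the site investigator's judgment (Protocol 8.3.1.5), so that table does not replace changes from screening or movements across normal limits. Likewise, every TEAE of any grade appears in the all-TEAE tables, so only the mild-versus-moderate split is lost there.

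**Size can be made to look larger.** Counting only hematology and urinalysis gives 12 of 23 (52%), but that leaves out the 21 chemistry tests, all of them summarized and including the electrolytes, creatinine and urea. Multiplying out results (600 subjects × 4 visits × 12 tests = 28,800) assumes full attendance and measures volume, not harm. The available text gives no diarrhea rate from which to size the severity gap.

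**The protocol's laboratory sentence fits numeric tests.** This is fair. Change from baseline has little meaning for dipstick or microscopy results. For those the missing item is counts and percentages by visit, which SAP 3.8.2 itself promises for categorical tests.

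**The table list has not been seen.** SAP Section 4 places it in a separate document, so a fuller severity table could appear there. The SAP wording points the other way.

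**Conclusion.** The point holds as an undeclared narrowing of descriptive safety reporting. Its firmer half is severity: one of three collected grades is tabulated where the protocol calls for tabulation by severity, and the mild-versus-moderate split cannot be recovered from the planned tables. The laboratory half is real but smaller: 12 of 44 tests (27%) lose by-visit descriptive summaries, keep the tabulation of clinically significant abnormalities, and have an uncertain place in the shift tables.

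This rests on the SAP meaning what it says in 3.8.1, and on the separate programming document not restoring the tables. No data are lost, so the tables could be produced later. Specifying them before unblinding avoids any suggestion that they were chosen after seeing results. The primary analysis, sample size and type I error are not affected.

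**What to change.** **SAP 3.8.1.** Tabulate all TEAEs and drug-related TEAEs by arm, SOC and PT, and maximum severity (mild, moderate, severe), using the most-severe-occurrence rule already there. Correct the sentence so that it refers to severity in general.

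**SAP 3.8.2.** Add the six numeric differentials to the by-visit summaries and the shift tables. For urine protein, glucose, ketones, blood, nitrite and microscopy, give category counts and percentages by visit and arm. If the sponsor prefers to leave any of these out, state that as a change from Protocol 10.7.7 with the reason. In either case, say explicitly whether each of the 12 tests enters the shift tables.

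**Cost.** Revised SAP wording and a few more tables from data already collected and graded, with no added work for sites or subjects.
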